Official Title of the study: **Randomized Controlled Trial of Web Based Tools to Improve Medication Continuity in Adolescents With ADHD**

NCT number: **NCT04386096**

Document name: **Statistical Analysis Plan**

Date of the document: **12/15/2021**

The results of the Web Based Tools study will be assessed as described in this document. This statistical analysis plan begins with an overview of the key components of the study, including its design, objectives, and outcomes measures. This is followed by a detailed description of the statistical analyses that will be utilized to address study hypotheses.

**1. Overview of study:** This study used a parallel group randomized control trial to test whether an intervention engages the proposed mechanism underlying medication continuity and improves outcomes. Adolescents and their parents that agreed to participate in the study were randomized to receive either the intervention (MeHealth for ADHD software with medication continuity tools) or the control group (MeHealth for ADHD software with no medication continuity tools). We used a stratified randomization procedure to ensure that the intervention and control groups were balanced with respect to the number of days covered with ADHD stimulant medication in the past year based on dispensing data. We planned to enroll a total of 44 adolescents aged 11-15 with ADHD with poor medication continuity from Cincinnati Children's Pediatric Primary Care Clinic (PPCC) in order to retain  $\geq 36$  subjects needed based on our sample size calculation.

**1.1 Study Objective:** Test a multi-component intervention that systematically identifies and targets aspects of the Unified Theory of Behavior Change (UTBC) model most relevant for each adolescent with poor ADHD medication continuity.

Working hypothesis 1: compared to the control group, the intervention group will have greater medication continuity as measured by number of days covered with medicine at the end of the study.

Working hypothesis 2: compared to the control group, the intervention group will have improved outcomes as measured by change in the Unified Theory of Behavior Change factors.

## 1.2 Outcome measures

### *Primary*

- Medication continuity as measured by proportion of days covered with medicine during the 4-month trial.
  - Number of days covered with medicine is calculated from audit of prescriptions dispensed.

### *Secondary*

- Change in pre-intention factors of Unified Theory of Behavior Change at baseline and approximately 4 months later.
  - Adolescent and parent self-report on a 5- or 7-point scale, depending on the item. Individual items measure specific attitudes, subjective norms, and perceived behavioral control. Higher scores indicate a stronger belief.
- Change in intention to take/give ADHD medicine regularly at baseline and approximately 4 months later.
  - Adolescent and parent self-report on 7-point scale. Higher scores indicate a stronger intention.
- Change in adolescent-report of medication barriers at baseline and approximately 4 months later.

- Adolescent self-report on Adolescent Medication Barriers Scale using 5-point Likert scale. Higher score means less barriers.
- Change in parent-report of medication barriers at baseline and approximately 4 months later.
  - Parent self-report on Parent Medication Barriers scale using 5-point Likert scale. Higher score means less barriers.
- Change in medication diversion at baseline and approximately 4 months later.
  - Adolescent self-report of the number of occasions of giving away, trading, or selling ADHD medicine to someone for whom it was not prescribed.
- Change in Decision Making Involvement Scale at baseline and approximately 4 months later.
  - Adolescent and Parent self-report. The scale contains the following subscales: "Child Seek" (e.g. child asks for an opinion or information from the parent), "Child Express" (e.g. child expresses an opinion or information to the parent), "Parent Seek" (e.g. parent asks for an opinion or information from child), "Parent Express" (e.g. parent expresses advice, an opinion, or information to the child), and "Joint/Options" (e.g. negotiation and brainstorming between child and parent). Each subscale produces a score which ranges from 1 to 4 with higher scores indicating more of that behavior.

### **1.3 Intervention Fidelity measures**

#### *Intervention group only*

- Fidelity to intended use of intervention components during the 4-month trial.
  - Proportion of intervention components completed relative to the components that were recommended by the portal based on adolescent/parent responses to the assessment battery.

### **1.4 Schedule of visits and time points of interest**

- Baseline survey (baseline, after consent, usually a few days after)
- Medication continuity over past year obtained at baseline
- End of study survey (4 months post study start date)
- Medication continuity at end of study (average of 4 months)

### **1.5 Data Management**

CCHMC CRC will guide data management for this project as described in the study protocol.

### **1.6 Interim Safety Analyses**

No interim analyses are planned for this study.

## **2. Statistical Reports**

### **2.1 Report Generation**

#### 2.1.1 Software

All statistical analyses will be performed using SAS version 9.4 (SAS Institute Inc., Cary, NC, USA) under Microsoft Windows operating system

Web Based Tools SAP

Version 1.1, 12/15/2021

pg. 2

## **2.2 Analysis Populations**

### **2.2.1 Screen Failures**

Subjects who are recruited but do not meet initial eligibility criteria and subjects who give informed written consent but after obtaining dispensing records are determined ineligible are considered screen failures. Screen failures will not be included in the analysis.

### **2.2.2 Completion**

Subjects will be considered to have completed the study once the patient completes the 4-month post survey or study end date on 5/24/21.

### **2.2.3 Outliers**

The data management and statistical analysis teams will identify subjects having data values that appear to be potential outliers. These values will be sent to the research coordinators for verification. Clear identification of a value as an outlier will be based on medical judgment as well as on statistical grounds. In the event that outlier values are identified, any analysis using the actual values will be followed by an analysis that reduces the outlier effect.

### **2.2.4 Missing data**

We will use pharmacy dispensing records to calculate our primary outcome for all study participants unless consent is withdrawn.

For secondary outcomes, missing outcome data could occur for several reasons such as item nonresponse, lost to follow-up, and data collection errors. The average score of the total number of available items within a factor score will be used to account for missing outcome data.

### **2.2.5 Protocol Violations/Withdrawals**

If a study participant is to be excluded/dropped from the study database and/or analysis, the PIs/coordinators will provide to the statistical analysis team the following: 1) the specific reason for dropout (e.g., withdrawal, protocol violation), in as much detail as possible; 2) who decided that the participant would be excluded; and 3) whether the exclusion involves some or all types of participation.

## **2.3 Statistical Report Contents**

The following section outlines the contents of the final statistical analysis. For all analyses, baseline is defined as the measurement collected during the baseline survey. Subjects who are enrolled in the study and are eligible will be analyzed in the groups to which they were allocated.

### **2.3.1 Description of study population**

#### Sample size:

The total number of subjects who are consented/registered and withdrawn will be given. A summary of subjects who were withdrawn will be provided.

### Demographics and Clinical Characteristics, Patient and Parent:

Demographic and clinical characteristics as measured at baseline will be summarized by trial arm.

Variables to be summarized are: parent age, parent race and ethnicity, parent sex, child sex, child age, child race and ethnicity. Variables will be summarized using descriptive statistics appropriate for each type of data item.

Baseline characteristics with large differences between groups will be included in analyses evaluating the effectiveness of the intervention.

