15. Client Satisfaction Questionnaire (CSQ) (Attkisson et al. 1982) is an 8-item unidimensional measure of client satisfaction with services. Psychometric properties, operating characteristics, and coefficient alpha (.93) are very strong for this measure which we will collect from adolescents and parents.
16. Decision Making Involvement Scale (DMIS) (Miller et al., 2012): is a 30-item scale to measure adolescent involvement in a decision. The five subscales are: “Child Seek” (child asks for an opinion or information from parent), “Child Express” (child expresses an opinion or information to parent), “Parent Seek” (parent expresses advice or opinion to child), “Parent Express” (parent expresses advice or opinion to child), and

“Joint/Options” (negotiation or brainstorming between parent and child). We will collect this measure from adolescents and parents.

DATA ANALYSIS

Hypothesis testing:

Each hypothesis examines part of the mechanism underpinning intervention impact on medication continuity.

Hypothesis #1: *Adolescents will use greater than 80% of relevant intervention components.* For each subject in the intervention group, we will calculate the proportion of **recommended** intervention components that were utilized by the subject during the study. The mean and 95% confidence interval (CI) will be computed to give a range estimate of the fidelity measure. To evaluate our hypothesis, we will utilize the computed CI to determine if 80% or greater is a plausible value, such that if the CI includes a value of 80% or greater we will reject the null hypothesis. We will also examine the temporal distribution of use for each of the recommended components.

Hypothesis #2: *Use of the intervention components will be related to improvements in the targeted UTBC factors.* Using a generalized linear model, we will test whether the intervention addressed the UTBC factors (i.e., pre-intention factor scales and ABMS/PBMS total and subscale scores). Model predictors will include a fixed effect indicator of time point (baseline or end of study). A significant effect of time point in the expected direction would indicate UTBC factor improvement.

Hypothesis #3: *Medication continuity will be higher in the intervention group compared to the control group.* We will compare the percentage of days covered with medicine using a two-sample t-test.

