Hypothesis #4: *Pre-post changes in UTBC factors will be related to increases in medication continuity.* We will calculate the change score for each relevant UTBC factor (end of study minus baseline) and the change score for medication continuity (percentage of days covered at end of study minus percentage of days covered in the 12 months prior to study). We will model the association between change in UTBC factor scores (independent variable) with change in medication continuity (dependent variable) using generalized linear mixed model. A significant effect of change in UTBC factor scores (beta coefficient) in the expected direction would indicate changes in UTBC factor scores were associated with medication continuity improvement.

Exploratory analyses:

We will conduct descriptive analyses to characterize rates of diversion at baseline and at the end of study using a McNemar's test to see if rates differ. We will summarize responses to the client satisfaction questionnaire descriptively as this may facilitate future dissemination.

Power and Sample Size:

The study would require a sample size of 18 for each group (i.e. a total sample size of 36), to achieve a power of 80% and a level of significance of .05 (two sided), to detect a difference in means between the intervention and the control groups of 15.7% (i.e. 66.2% vs. 50.5%) on the percentage of days covered with medicine assuming a pooled standard deviation of 16.5. Due to the low intra-class correlations observed in previous studies of ADHD medication continuity (ICC = 0; [name] et al. 2018), the analyses will not account for the nesting of patients within physicians. We will recruit 44 patients to ensure that 36 are retained at the end of the study. A retention rate of 80% (36/44) is conservative in light of the 12-month retention rate of 92% achieved by [name] in his current trial. We will use a stratified blocked randomization procedure to ensure baseline medication continuity is evenly distributed in both arms.

Scientific Rigor:

The RCT is a rigorous design to test efficacy of our intervention. We will explicitly address whether the intervention engages the mechanism underlying medication continuity and therefore warrants further testing in a future larger trial. Our preliminary data strongly supports the importance of the problem, intervention targets identified, and the feasibility of the approach in our hands.

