#### 2.3.2 Primary outcome analysis

*Primary outcome:* Medication continuity as measured by proportion of days covered with medicine during the 4-month trial.

- Number of days covered with medicine is calculated from audit of prescriptions dispensed.

For the primary outcome, the dependent variable will be a proportion of the number of days covered with ADHD medicine during the 4-month trial. Differences between intervention and control groups on this outcome will be evaluated using a two-sample t-test or Wilcoxon rank sum test.

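### SAP 2.3.1 selects covariates for the effectiveness analyses by chance baseline imbalance, with no threshold, no model that can carry them, and no statement of which result is primary

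*SAP*

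**What the plan says.** SAP 2.3.1, under the heading on demographics and clinical characteristics, first lists what will be tabulated by arm: "Variables to be summarized are: parent age, parent race and ethnicity, parent sex, child sex, child age, child race and ethnicity". It then gives an instruction: "Baseline characteristics with large differences between groups will be included in analyses evaluating the effectiveness of the intervention". It gives no measure of difference, no cut-off and no regression model.

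For the primary outcome, SAP 2.3.2 says: "Differences between intervention and control groups on this outcome will be evaluated using a two-sample t-test or Wilcoxon rank sum test". Protocol Hypothesis #3 is narrower: "We will compare the percentage of days covered with medicine using a two-sample t-test". The Protocol's sample size rests on that unadjusted comparison. SAP 2.3.3 names a paired t-test for each secondary outcome, which carries no covariates either.

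Prior-year days covered by medicine is verified from dispensing data before randomisation and is the stratification factor (Protocol, Study Design and Power and Sample Size; SAP 1). SAP 1.4 lists it among the data obtained at baseline. Neither document names it as a covariate in the primary analysis.

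**The concern.** In a randomised comparison any observed baseline difference arises by chance. Its size says nothing about whether the variable predicts days covered, and predicting the outcome is the reason to adjust. A covariate that is imbalanced but not prognostic costs precision, because it is correlated with arm and explains none of the outcome. The rule also tends to miss the covariate the design itself treats as important: stratifying on prior-year days covered makes a large difference in that variable unlikely.

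The rule cannot be followed inside the named tests. Once a difference is judged large, a model the SAP does not name has to be run, and a reader cannot tell whether that model or the t-test supplies the headline result. At stake are some power and the assurance that the primary p-value comes from one analysis fixed in advance.

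**Working it through.** **Inputs.** From the Protocol, Power and Sample Size: difference 15.7 points (66.2% vs 50.5%), "assuming a pooled standard deviation of 16.5", two-sided 0.05, 80% power, 18 per group, 44 recruited (22 per arm). From SAP 2.3.1: 6 listed characteristics, or 8 if each race and ethnicity item counts as two. Assumptions, because the documents give no figure: the characteristics are independent, normal theory is adequate for the categorical ones, and *large* is tried at 0.25, 0.5 and 0.8 SD.

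**1. The plan's own figure.** n = 2 × (1.96 + 0.842)² × (16.5/15.7)² = 2 × 7.85 × 1.1045 = 17.3, so 18 per arm. This reproduces. At 18 per arm, power is 81.4% by the normal approximation and 79.2% by the noncentral t; at 22 per arm it is 86.9% by the noncentral t.

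**2. How often the rule fires.** For one variable with n per arm, p = 2 × [1 − Φ(s√(n/2))]. For k variables the chance of at least one is 1 − (1 − p)^k. Example: s = 0.5, n = 18 gives Φ(1.5), p = 0.134, and with k = 8, 1 − 0.866⁸ = 68%.

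| Threshold | 18 per arm, k = 6 / 8 | 22 per arm, k = 6 / 8 |
|---|---|---|
| 0.25 SD | 97% / 99% | 96% / 98% |
| 0.5 SD | 58% / 68% | 46% / 56% |
| 0.8 SD | 9% / 12% | 5% / 6% |

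If *large* meant p < 0.05, the chance would be 1 − 0.95⁶ = 26% or 1 − 0.95⁸ = 34%.

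**3. Power if the flagged covariates are non-prognostic.** At 0.5 SD with 8 variables, the simulated mean variance inflation when the rule fires is 1.21 (18 per arm) or 1.16 (22 per arm). The planned standardised effect is 15.7/16.5 = 0.952. Dividing it by √1.21 takes power from 79% to about 71%; dividing by √1.16 takes it from 87% to about 82%. Averaged over all trials the loss is 0.68 × (79 − 71) ≈ 5 points, or 0.56 × (87 − 82) ≈ 3 points.

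Direct simulation agrees. With 6 covariates and 18 per arm (8,000 trials per scenario), power goes from 78.5% to 71.3% at 0.25 SD and from 78.8% to 74.6% at 0.5 SD. With 8 covariates and thresholds from 0.25 to 0.8 SD, it goes from 78% to 70-77% (18 per arm) and from 88% to 82-88% (22 per arm). The drop is up to about 9 points at 0.25 SD and about 1 point at 0.8 SD.

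**4. Type I error.** With a fixed threshold applied mechanically, simulated error is 4.2-5.0% (6 covariates, 18 per arm) and 4.6-6.0% (8 covariates, 18 and 22 per arm). Monte Carlo standard error at 8,000 runs is √(0.05 × 0.95/8,000) = 0.24 points. If the analyst may report the better of the t-test and the adjusted model, error is 6.2-7.2% at 18 per arm. If the threshold may also be chosen between 0.25 and 0.8 SD, it is about 7-8%.

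**5. A pre-fixed covariate.** At 18 per arm, one covariate fixed in advance gives simulated power of 87-89% if it correlates 0.5 with the outcome, against 78-79% under the imbalance rule and 78-80% for the t-test. If the correlation is 0, the fixed covariate gives 77-78% and the rule 71-75%. Both correlations are assumed.

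**The case against.** Adjusting for visible imbalance is common, and several stronger readings of this text do not hold.

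- A reader might infer that the rule itself inflates the false-positive rate. It does not: applied mechanically at a fixed threshold, it leaves type I error near 5%. The 6-8% needs a free choice among results, which the SAP nowhere grants.
- A reader might infer that a regression replaces the named test. The SAP does not say so, and the adjusted analysis could be meant as an addition. What stands is that the SAP leaves this open.
- A reader might infer from the dates (SAP version 1.1 of 12/15/2021, study end 5/24/21) that the covariates were chosen with outcomes in view. The dates show only that this version followed the end of the study. They do not show that anyone had seen outcomes by arm or that the sentence was new.
- A reader might infer that only demographics are eligible. The list is of variables to be summarised, and the adjustment sentence speaks of baseline characteristics generally.

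The size also depends on generous assumptions. Parent and child race and ethnicity are plainly related, so independence overstates the trigger rate. At 0.8 SD the rule would rarely fire. The primary outcome comes from dispensing records for everyone who does not withdraw consent (SAP 2.2.4), so 22 per arm is the more relevant case. With one covariate correlated 0.5 with the outcome, the rule costs essentially no power relative to the t-test (78-79% against 78-80%).

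These points limit the harm. They do not supply the missing threshold, model or primary result, or make imbalance a sound basis for selection.

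**Conclusion.** The point holds as a defect of specification with a modest cost. The instruction is mandatory in wording, selects on the wrong criterion and cannot be carried out in the tests the SAP names. Depending on a word the SAP leaves undefined, it would apply in almost no trials or almost all: about 5-12% at 0.8 SD, 46-68% at 0.5 SD and 96-99% at 0.25 SD. The average power loss is about 1 point, 3-5 points and up to 9 points respectively, if the flagged covariates are non-prognostic, and smaller if any of them predicts the outcome. Type I error is a concern only through discretion, with about 6-8% as a worst case. All of this rests on 6 to 8 independent characteristics, normal approximations and 18 to 22 per arm. Confidence is high on the undefined rule and its conflict with the named tests, and lower on the exact size.

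**What to change.** - **SAP 2.3.1:** delete the sentence on including characteristics with large differences. Keep the baseline table as description.
- **SAP 2.3.2:** name one primary model whose covariates are fixed whatever imbalance is seen. A linear model (ANCOVA) of proportion of days covered on arm, adjusted for prior-year days covered, would serve: the variable is the stratification factor and is already collected. It should take the place of the t-test or Wilcoxon wording, since those tests cannot hold the covariate.
- **SAP 2.3.3:** apply the same fixed-covariate principle to the between-arm secondary analyses, with a model that can carry the covariates.
- **Sensitivity analysis:** allow an imbalance-adjusted model only if labelled as such, and state that it cannot replace the primary result.

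The cost is SAP wording; no new data are needed. If prior-year days covered turned out unrelated to the outcome, the price would be about a point of power at 18 per arm. A striking chance imbalance would be handled only in the sensitivity analysis, which is a small downside.

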#### 2.3.2 Primary outcome analysis

*Primary outcome:* Medication continuity as measured by proportion of days covered with medicine during the 4-month trial.

- Number of days covered with medicine is calculated from audit of prescriptions dispensed.

For the primary outcome, the dependent variable will be a proportion of the number of days covered with ADHD medicine during the 4-month trial. Differences between intervention and control groups on this outcome will be evaluated using a two-sample t-test or Wilcoxon rank sum test.

